1. **Project title:** Danish Pulses: Tasty, Healthy, and Safe Danish Pulses with Added Value for The Users
1. **Danish title:** Dansk Bælg: Velsmagende, sunde og sikre danske bælgfrugter med merværdi for brugerne

GUDP grant number: 34009-23-2191

2. Rationale and purpose

Fermentation of legumes has the potential to enhance the health benefits associated with increasing daily legume consumption to 100 grams, as recommended by the Danish Veterinary and Food Administration (1). Despite this, the current average daily intake among Danes remains as low as 2–3 grams (1). Legumes are widely recognized for their contribution to satiety, thereby supporting weight management and their role in the prevention of non-communicable diseases (2–6). These health-promoting effects are largely attributed to their content of bioactive compounds, including phenolics, peptides, and dietary fiber, which positively modulate the gut microbiota (7,8). However, legumes also contain antinutritional factors such as lectins, phytic acid, and protease inhibitors, which can hinder the bioavailability of essential nutrients, including proteins, vitamins, and minerals, ultimately diminishing the nutritional value of legume-based foods (7–10).

Food processing techniques—particularly fermentation—offer promising strategies to mitigate these antinutrients, as fermentation has been shown to reduce antinutrient content by 70–90%, depending on the method and substrate used (10–13). This process involves microbial metabolism, in which carbohydrates are oxidized to generate energy while simultaneously enhancing the bioavailability of minerals in plant-based foods (10–13). Fermentation has also been demonstrated to increase the levels of free amino acids, including essential amino acids such as lysine, methionine, and tryptophan, in cereals (14), and similar effects may be observed in legumes—though this remains to be fully elucidated (15).

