Participants in the treatment groups are given two weeks of LAB-fermented or unfermented foods, containing 100 g of legumes, including fava beans, peas, and lentils. Fermented and unfermented legumes will be provided and packed as standardized food items to their habitual meals e.g. as hummus, or pasta with legume flour, adding up to 100 g of legumes per day, seven days a week, for two weeks. These test foods can be eaten throughout the day; however, intake of other legumes, except those included in the foods, should be avoided. If participants eat other legumes, this should be noted and accounted for in data analysis. If participants do not consume the full 100 g of legumes, they must weigh the leftovers and take a photo of the remaining food and report to the researchers.

Primary outcome:

Continuous Glucose Monitoring

Continuous Glucose Monitoring (CGM) will be measured in real-time and intermittently scanned CGM (isCGM) bi-weekly with an isCGM sensor (model Abbott Freestyle Libre PRO). This method is a minimally invasive method, as the sensor is placed on the participant's arm (26–30), by participants themselves after careful instructions, incl. videos. The Abbott Freestyle Libre PRO is blinded to the participants to avoid habitual changes, and it measures CGM in real-time throughout the entire 14-day period. The study follows the Standardized CGM metrics for Clinical Care, and the 14-day duration is aligned with the international recommendations (26,30). To ensure accurate and meaningful interpretation of CGM, adequate glucose data is collected according to the recommendation (70% of data from 14 days) (26,30). Data from participants with a CGM activity < 70% will be analyzed with the intention to treat principles.

Secondary Outcomes

The secondary outcome includes changes in inflammation, cholesterol, long-term blood glucose levels, systolic and diastolic blood pressure, body composition, the fecal microbiomes and metabolome, and dietary intake. Digestive abnormalities will also be assessed.

Inflammation monitoring

Fasting C-reactive proteins (CRP) monitoring will be measured at baseline, 14 days, and at day 28 by a finger prick test using a QuickRead go PLUS Instrument (#154580-4).

Cholesterol monitoring

Fasting cholesterol monitoring will be conducted at baseline, 14 days, and at day 28 by a finger prick test using a QuickRead go PLUS Instrument (#154580-4).

Long-term blood glucose monitoring

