including a thorough written introduction(33,34). Fecal pH will be determined by mixing fecal matter 1:2 with sterile MilliQ-water after which pH is measured. Total fecal DNA will be extracted using standard methods. The gut microbial metagenome will be determined by shotgun high-throughput sequencing using long-read Oxford Nanopore-based sequencing(33,34). Before any further bioinformatics processing the raw reads will be purged of any human DNA-related sequences.. Fecal short chain fatty acids (SCFA) and other fecal metabolite concentrations, incl. free amino acids, are determined using high-field nuclear magnetic resonance NMR (34) on fecal samples..

Dietary intake

Data on dietary intake will be collected by three-day dietary records with photos to evaluate adherence to the intervention. The dietary records will be collected once during the control period and once during the intervention period. Photos will be used for main meals and leftovers of legumes.

Physical activity will also be documented as part of the dietary records and used to estimate energy expenditure. Furthermore, data on dietary intake will be used to assess compliance with the intervention.

Digestive abnormalities

Digestive abnormalities are identified through IBS symptoms and will be assessed using self-reported questionnaires at baseline, follow-up 1, and 2, using the IBS Severity Scoring System (IBS-SSS) for assessment of the following symptoms: abdominal distension, abdominal pain, satisfaction with bowel habits, and the extent to which symptoms affect the quality of life (QoL) (35).

Overall data collection

Table 1: Data collection

Variables	Methods	Baseline Day 0	Follow-up 1 Day 14	Follow-up 2 Day 28
Age		x		
Sex		x		
Bio markers				
Blood glucose	Continuous blood glucose levels by glucometer: Abbott Freestyle Libre PRO	x	x	x
Cholesterol levels	Prick-test	x	x	x
C-reactive protein	Prick test	x	x	x
Long-term blood glucose	Prick test	x	x	x
Blood pressure	Systolic and diastolic blood pressures	x	x	x
Body composition				
Body composition incl. body weight, kg	Body Impedance Analytics (BIA)	x	x	x
Fat mass (FM), kg		x	x	x
Fat free mass (FFM), kg		x	x	x
Height, meters	Dynamometer	x		
Body Mass Index (BMI)	BMI is calculated by dividing weight (kg) by height (m) squared (kg/m ²).	x	x	x

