For ¹H NMR spectral data, fecal metabolites are assigned, and their concentrations are quantified using the Chenomx software. Subsequently, statistical analysis will be conducted on the individual metabolites as continuous variables are described above.

5. Risks, side effects, and disadvantages in the short and long term

In the study, no serious adverse events or risks are expected. There are no known serious adverse effects associated with the consumption of either non-fermented or fermented legumes in healthy adults, and the official dietary guidelines recommend an intake of 100 g of cooked legumes per day. All participants participate voluntarily and can withdraw from the study at any time. All participants are informed about the product content, and potential participants with food allergies or intolerances are excluded before starting the study.

The finger-prick test is a simple and nearly painless tool to measure inflammation, cholesterol, and blood glucose. No blood is collected, and the test is performed by trained researchers. A disinfectant is used to reduce the already small risk of bleeding, bruising, or infection.

Stool samples is safe to collect when EasySampler is used. Only a small sample is needed (approximately 10 g). There is no health risk when following the instructions.

This project meets the guidelines of the Declaration of Helsinki II, as well as the guidelines of the Regional Ethics Committee.

SJ-1132-120770, Version 3, 16-02-2026

The study has been submitted to the Science Ethics Committees for Region Zealand
j.nr.: SJ-1132-120770.

The study is covered by the Danish Patient Compensation scheme (In Danish: Patienterstatningen)

6. Biological material is collected.

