The results obtained will be published in anonymous form in international scientific journals and may be presented at conferences. Positive, negative, and inconclusive results will be published. If, contrary to expectations, the results are not published in a scientific journal, they will be published on www.clinicaltrials.gov and www.clinicaltrialsregister.eu

13. Ethics In the study, no serious adverse events or risks are expected. There are no known serious adverse effects associated with the consumption of either non-fermented or fermented legumes in healthy adults. All participants are informed about the product content, and potential participants with food allergies or intolerances are excluded before enrollment. . This project meets the guidelines of the Declaration of Helsinki II, as well as the guidelines of the Regional Ethics

SJ-1132-120770, Version 3, 16-02-2026

Committee. The research project has been submitted to the Science Ethics Committees for Region Zealand j.nr.:SJ-1132-120770.

a. Why the therapeutic benefit for the subjects or future patients justifies the studies

Danish pulses is a project aimed at getting more Danish-grown legumes—such as beans, peas, and lentils—into the food we eat daily. Legumes have a distinctive composition of proteins, – which can replace some of the meat in a meal, dietary fiber, which supports digestion and provides longer-lasting satiety, and carbohydrates. This combination makes legumes particularly interesting from a health perspective. The fiber and protein content may help slow the rise in blood sugar after a meal and contribute to satiety for a longer time.

The project covers the entire “journey” of legumes—from field to plate—and works with several different species and varieties. The knowledge generated from the study may therefore be relevant to many Danes and support a greener future.

[figure not shown]
13. Information regarding compensation

See. Pkt. 10.

Timeline perspective

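### Apart from the digestive questionnaire, the protocol has no adverse-event record, so sensor, finger-prick and non-digestive food reactions would go uncounted

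*Protocol*

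**What the plan says.** Section 5 (Risks, side effects, and disadvantages) opens with "In the study, no serious adverse events or risks are expected" and continues "There are no known serious adverse effects associated with the consumption of either non-fermented or fermented legumes in healthy adults". Section 13 (Ethics) makes the same statements. Neither section says how an event, if one occurred, would be asked about, recorded or reported.

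Two procedures that carry some risk are described. For the finger prick, section 5 says "A disinfectant is used to reduce the already small risk of bleeding, bruising, or infection". For the glucose sensor, section 3 (Continuous Glucose Monitoring) says "This method is a minimally invasive method, as the sensor is placed on the participant's arm" and that it is applied "by participants themselves after careful instructions, incl. videos". Section 5 does not mention the sensor.

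For digestive symptoms there is a plan. Section 3 (Secondary Outcomes) says "Digestive abnormalities will also be assessed", and the subsection on digestive abnormalities does so "using the IBS Severity Scoring System (IBS-SSS) for assessment of the following symptoms: abdominal distension, abdominal pain, satisfaction with bowel habits", together with the effect on quality of life. Table 1 schedules this questionnaire at Days 0, 14 and 28. No other row of Table 1 concerns harm.

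Section 8 (Processing of personal data) confines what is transferred to the secured drive to the information listed earlier in the protocol. The project title reads "Tasty, Healthy, and Safe Danish Pulses with Added Value for The Users".

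**The concern.** The protocol names possible harms (bleeding, bruising and infection from the finger prick), uses a self-applied sensor for the primary outcome, and feeds participants a product in a field that section 2 itself calls relatively novel. Yet outside the digestive questionnaire, nothing prompts anyone to ask about a reaction. If the plan is followed as written, an absence of reported events would mean only that none was asked for.

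Two features of the protocol make informal reporting a poor substitute. Section 10 pays participants only if they complete the whole study, which gives someone with a mild reaction a reason not to mention it. Later reconstruction is also closed off: section 7 uses no patient records, and section 8 destroys the code file once data collection ends.

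Three things are at stake. The first is a descriptive count of harms by arm. The second is the reason why primary-outcome glucose data are missing for a participant. The third is information on why people stopped, which matters for the first planned paper in section 12, a feasibility study of 100 g of legumes per day.

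**Working it through.** **Where a harm could be recorded.** Each type of event is set against the collection items in section 3 and Table 1.

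| Event | Item that would capture it |
|---|---|
| Distension, abdominal pain, bowel dissatisfaction, effect on quality of life | IBS-SSS, Days 0, 14, 28, both arms |
| Sensor-site reaction | None |
| Sensor data loss | Visible through the 70% activity criterion; cause not recorded |
| Finger-prick bleeding, bruising, infection | None |
| Non-digestive reaction to test food, acute illness | None |
| Uneaten test food | Leftovers weighed, photographed and reported; no reason asked |
| Early stopping | Withdrawal is allowed; no reason recorded |

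**The plan's own figure.** The number of people in whom harms could be counted is 50 (25 per group), from the sample size paragraph in section 3. Inputs there: difference 9 mg/dL, SD 10 to 11 mg/dL, power 0.80, significance level 0.05 (taken as two-sided, which is not stated), dropout 10%. Per arm, n = 2 × (1.960 + 0.842)² × SD² / 9², rounded up, then divided by 0.9 and rounded up:

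- SD 10: 20, then 23 per arm (46 in total)
- SD 10.5: 22, then 25 per arm (50 in total, as stated)
- SD 11: 24, then 27 per arm (54 in total)

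The stated 50 is reproduced at the middle of the given SD range.

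**Exposure without an event record.** Test food: 50 × 14 days = 700 person-days. Finger-prick visits: 50 × 3 = 150. Sensor wears: 50 × 2 = 100, assuming one sensor per 14-day period.

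**What recording would give.** If events were asked for and none occurred, the one-sided 95% upper bound on the true rate is 1 − 0.05^(1/n):

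- n = 25 (one arm): 11.3%
- n = 22 (one arm after 10% dropout, 25 × 0.9 = 22.5, rounded down): 12.7%
- n = 50 (both arms): 5.8%

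The probability of seeing at least one event of true rate p is 1 − (1 − p)^n. The rates are illustrative and do not come from the protocol.

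| p | n = 25 | n = 50 |
|---|---|---|
| 1% | 0.22 | 0.40 |
| 5% | 0.72 | 0.92 |
| 10% | 0.93 | 0.995 |

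A systematic question would probably pick up a common reaction and would usually miss a rare one. Without the question, no bound of any kind can be stated.

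**The case against.** The case on the other side is substantial, and much of it stands.

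- A reader might infer that all food harms go uncounted. The protocol does not support that. Digestive intolerance, the most plausible harm of 100 g of legumes a day, is measured against baseline and between arms at all three visits. What remains is that the IBS-SSS is a symptom score at fixed visits: it carries no onset date or seriousness, and it covers no non-digestive reaction.
- A reader might infer that the trial plans a safety conclusion it cannot support. It does not. The hypotheses in section 2 concern glucose, inflammation, cholesterol, microbiome, short-chain fatty acids and body composition, and neither paper in section 12 is a safety paper. The word safe stands only in the title of the wider project. Nor would recording rescue such a conclusion, given an upper bound of about 11% per arm.
- A reader might infer that sensor failure would be invisible. The 70% activity criterion shows the data loss for each participant. Only its cause is missing.
- A reader might infer that events would go unnoticed. Section 11 lets participants reach the principal investigator throughout, section 3 has them report leftovers, and section 8 has data documented continuously and reviewed. Contact pages were also removed from the copy at hand, so no missing contact route is alleged. These routes are not an event record, and section 8 keeps only the listed data.
- The sentence in section 5 is about serious events in healthy adults eating an officially recommended amount. Known legume allergy or intolerance is an exclusion, and trained researchers perform the finger prick. As an expectation the sentence is reasonable; it does not replace recording.

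The statistical analysis plan is not shown, but it could not fill this gap, because what is collected is fixed in the protocol.

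**Conclusion.** The point holds in a narrow form. Beyond the IBS-SSS there is no adverse-event record, so sensor-site reactions, finger-prick complications, non-digestive reactions to test food, and the reasons for sensor loss and early stopping would not be counted by arm. The trial could then offer no descriptive harms count.

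The primary comparison, the randomisation and the sample size are unaffected. The gain from closing the gap is also limited: the bounds assume that every participant is asked, that no event occurs, and that 25 per arm (or 50 pooled) are observed. Counts from this trial would be descriptive and would not demonstrate safety. The change is still worth making, because it is cheap, bears on participant safety, and cannot be made after the data are collected.

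**What to change.** - Add an **Adverse events** row to Table 1 at Day 14 and Day 28. Use one open question plus tick boxes for sensor-site reaction, finger-prick complication, reaction to test food, acute illness and other, each with onset date, severity and seriousness.
- Record the cause of any sensor loss.
- Record the reason for early stopping if the participant volunteers it. Section 11 lets participants stop without giving a justification, so the reason cannot be required.
- Report control-period events for all enrolled participants. Test food starts only at Day 14, so a report restricted to those who received it would miss sensor reactions in the first two weeks. Report intervention-period events by randomised arm for everyone who received test food.
- Reword sections 5 and 13 to say that serious events are not expected and that any events will be recorded.
- Present the counts as descriptive.

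How an individual event is handled stays with the investigator. The cost is a few minutes at visits that already take place and one small table in the report. Inclusion starts in September 2026 and this version is dated February 2026, so there is time to add it beforehand.
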